10.2 Baseline (Week 0)

At Visit 2 (Baseline Visit), the following procedures and assessments will be performed:

- Medical history update
- Concomitant medication use assessed
- Rescue medication supplies returned, appropriate use assessed, and compliance/accountability performed
- Adverse events assessed
- Sitting vital signs (blood pressure and pulse after 5 minutes)
- Brief physical examination
- Electrocardiogram after 5 minutes in supine position
- Urine pregnancy test for females of childbearing potential
- Urine drug test

- Breathalyzer test for alcohol
- Urine sample for urinalysis
- Bedside Sensory Testing Kit
- Pain scores reported by subjects during the Screening Period and diary compliance evaluated by the interactive response technology system for raw score and for variability among scores by automated transmission of pain scores from the handheld devices

Subjects who continue to meet all entry criteria and are randomized by the interactive response technology system will undergo the following procedures and assessments:

- Blood samples for fasting (8 hours) serum chemistry and hematology
- HADS
- S-STS
- BPI-DPN
- SF-MPQ-2
- QOL-DN
- Insomnia Severity Index
- Investigational product dispensed
- Rescue medication dispensed

Subjects will be reminded on how to record their pain on the device

Subjects will also be reminded about appropriate expectations around their participation in a clinical study

Review of these educational materials may be repeated for some or all subjects depending on findings of an ongoing blinded data review (e.g., if pain score variability is increased on a subject or site level. On each day until returning to the study site at Week 2, subjects will record the following on the handheld device:

- At bedtime: average pain intensity, worst pain intensity, pain on walking, and use of rescue medication during the past 24 hours.
- Upon waking: DSIS

The investigative site staff will contact study subjects by telephone one week following Week 0 to reinforce the diary completion and assess adverse events.

Subjects will be instructed to return to the study site at Week 2.

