- 11. HIV infection, hepatitis, or other ongoing infectious disease that the investigator considers clinically significant.

- 12. Concomitant use of antiepileptic drugs, non-steroidal anti-inflammatory drugs (except cardiac preventive acetylsalicylic acid), opioids, muscle relaxants, dextromethorphan (except low dose intermittent use for cough), tramadol, topical lidocaine, topical capsaicin, and selective norepinephrine reuptake inhibitors. Subjects are allowed to enter with a maximum of 1 allowed analgesic medication for neuropathic pain that has been taken at a stable dose for at least 1 month (30 days) prior to Visit 1. Allowed analgesics may not be *N*-methyl-D-aspartate receptor ligands, must be non-opioid and non-sedative, and must not interfere with subjects' pain reporting. Tricyclic antidepressants may be continued if designated as the single analgesic medication for the treatment of pain.
- 13. History of or current substance abuse disorder as defined by Diagnostic and Statistical Manual of Mental Disorders Fifth Edition.
- 14. Recreational and/or medicinal marijuana use within the past 6 months.
- 15. Positive urine drug screen for marijuana, opioids, benzodiazepines inconsistent with current prescriptions, or breathalyzer test for alcohol at Visit 1.
- 16. Positive urine drug screen for marijuana, opioids, benzodiazepines inconsistent with current prescriptions, or breathalyzer test for alcohol at Visit 2.
- 17. Sensitivity to, allergy to, or concomitant use of *N*-methyl-D-aspartate receptor ligands including ketamine, amantadine, dextromethorphan (except low dose intermittent use for cough), memantine, methadone, dextropropoxyphene, and/or ketobemidone.
- 18. Amputations of lower extremities (toe amputation is allowed).
- 19. Any condition, including serious medical conditions that could interfere with the ability of the subject to participate in the study or could confound study assessments.
- 20. Subjects with hypersensitivity to multiple medications, in the opinion of the investigator.
- 21. Subjects who meet the criteria for suicidal intent, plan and/ or behavior by scoring 3 or 4 on Questions 2 or 13, or 2 or higher on any Question 1a (only if 1b is coded YES), 3, 4, 5, 6, 7, 8, 9, 10, 11, 12, or 14 based on the S-STS at Visit 1 or Visit 2.

Waivers to the exclusion criteria will NOT be allowed.

Test product, dose and mode of administration, batch number:

NYX-2925, oral capsules, 2 capsules once daily by mouth.

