At Visit 2 (Baseline Visit), study personnel will verify eligibility with the inclusion and exclusion criteria when the subjects are on site, and prior to randomization. Pain scores reported by subjects during the Screening Period will be evaluated by the interactive response technology system for raw score and for variability among scores after transmission of pain scores from the handheld devices to determine eligibility. The interactive response technology system will notify the site if the subject is "Eligible" or "Not eligible". No other information will be provided.

Subjects whose mean of the daily average pain intensity score during the preceding 7 ± 1 days is within the protocol-defined algorithm (Section 12.2) and with adequate compliance with daily diary completion will be eligible for randomization. The absolute pain score and variability among scores, as well as the actual percentage required for diary compliance, will be masked to investigators and subjects. The appropriate use of rescue medication will be assessed by inventory of the returned caplets, as well as by subject interview. Subject eligibility for randomization into the study based on these variables will be communicated to the investigator via the interactive response technology system.

Subjects will again be asked a non-leading question to assess potential adverse events, for example, "Have you experienced any new or changes symptoms since we last asked/since your last visit?" Use of concomitant medications will be documented. Vital signs (blood pressure and pulse) will be measured after sitting for 5 minutes and a 5-minute electrocardiogram will be performed. Medical history will be updated and a brief physical examination performed. Blood and urine samples will be collected for chemistry, hematology, and urinalysis testing. Subjects will undergo drug and alcohol screen using a local urine testing kit and breathalyzer, respectively. Subjects who test positive for marijuana, opioids, benzodiazepines inconsistent with current prescriptions, or alcohol, will not be allowed to continue in the study. Female subjects of childbearing potential will be tested for pregnancy using a local urine testing kit and will be counseled to continue using highly effective contraception.

Eligible subjects will be randomized to receive either NYX-2925 or placebo for 4 weeks. Investigators and subjects will be masked to the randomization allocation.

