Subjects will be dispensed a 2-week supply of investigational product and instructed to take 2 capsules by mouth once daily. Subjects will also be re-dispensed acetaminophen to use as rescue medication for DPN pain; instructions not to exceed 2 g/day will be reinforced.

Subjects will be instructed to continue entering their average pain intensity, worst pain intensity, pain upon walking, and whether they used rescue medication over the past 24 hours into their study-issued handheld devices every night. Every morning upon awakening, subjects will complete the DSIS via their study-issued handheld device. Pain diary compliance will be reviewed at each study visit by the study staff, and reporting instructions will be reinforced.

Quantitative sensory testing will be done using the Bedside Sensory Testing Kit. The following scales will be completed at the Baseline Visit: BPI-DPN, the SF-MPQ-2, the QOL-DN, the HADS, the Insomnia Severity Index, and the S-STS.

One week following the Week 0 visit, subjects will be contacted by telephone for an assessment of adverse events and to reinforce diary completion. Adverse events will be assessed by asking the subject a non-leading question.

Treatment Period (Week 2, Visit 3)

Subjects will return to the clinic at the end of Week 2 for assessment of compliance with study medication, use of rescue medication, and be dispensed the final 2-week supply of investigational product and rescue medication for DPN pain. Pain diary compliance will be reviewed by the study staff, and reporting instructions will be reinforced. Adverse events will be assessed by asking the subject a non-leading question; for example, "Have you experienced any new or changed symptoms since we last asked/since your last visit?" Use of concomitant medications will be documented. Vital signs (sitting blood pressure and pulse after 5 minutes) will be measured. Blood samples will be collected for liver function testing. Female subjects of childbearing potential will be counseled to continue using highly effective contraception.

Subjects will be instructed to continue entering their average pain intensity, worst pain intensity, pain upon walking, and rescue medication use over the past 24 hours into their study-issued handheld devices every night. Every morning upon awakening, subjects will complete the DSIS via their study-issued handheld device.

Scales to be completed at the Week 2 visit include the PGI-C, the S-STS, and the Insomnia Severity Index.

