- 11. Human immunodeficiency virus (HIV) infection, hepatitis, or other ongoing infectious disease that the investigator considers clinically significant.
- 12. Concomitant use of antiepileptic drugs, non-steroidal anti-inflammatory drugs (except cardiac preventive acetylsalicylic acid), opioids, muscle relaxants, dextromethorphan (except low dose intermittent use for cough), tramadol, topical lidocaine, topical capsaicin, and selective norepinephrine reuptake inhibitors. Subjects are allowed to enter with a maximum of 1 allowed analgesic medication for neuropathic pain that has been taken at a stable dose for at least 1 month (30 days) prior to Visit 1. Allowed analgesics may not be *N*-methyl-D-aspartate receptor ligands, must be non-opioid and non-sedative and must not interfere with subjects' pain reporting (Section 8.7). Tricyclic antidepressants may be continued if designated as the single analgesic medication for the treatment of pain.
- 13. History of or current substance abuse disorder as defined by Diagnostic and Statistical Manual of Mental Disorders Fifth Edition.
- 14. Recreational and/or medicinal marijuana use within the past 6 months.
- 15. Positive urine drug screen for marijuana, opioids, benzodiazepines inconsistent with current prescriptions, or breathalyzer test for alcohol at Visit 1.
- 16. Positive urine drug screen for marijuana, opioids, any benzodiazepines inconsistent with current prescriptions, or breathalyzer test for alcohol at Visit 2.
- 17. Sensitivity to, allergy to, or concomitant use of *N*-methyl-D-aspartate receptor ligands including ketamine, amantadine, dextromethorphan (except low dose intermittent use for cough), memantine, methadone, dextropropoxyphene, and/or ketobemidone.
- 18. Amputations of lower extremities (toe amputation is allowed).

- 19. Any condition, including serious medical conditions that could interfere with the ability of the subject to participate in the study or could confound study assessments.
- 20. Subjects with hypersensitivity to multiple medications, in the opinion of the investigator.
- 21. Subjects who meet the criteria for suicidal intent, plan, and/or behavior by scoring 3 or 4 on Questions 2 or 13, or 2 or higher on any Question 1a (only if 1b is coded YES), 3, 4, 5, 6, 7, 8, 9, 10, 11, 12, or 14 based on the S-STS at Visit 1 or Visit 2.

Waivers to the exclusion criteria will NOT be allowed.

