10.1 Screening Period (Week -4 to -1)

The subject will be asked to provide informed consent for this study before any required procedures are performed. Subjects will also be asked to sign an additional consent for their inclusion in a subject registry database. Adverse event collection will begin at the time of informed consent.

After the informed consents are signed, the following procedures and assessments should be completed at Visit 1:

- Confirmation of diabetic peripheral neuropathy by the following assessments:
 - Michigan Neuropathy Screening Instrument
 - o Masquerading Disorders Tool
 - o American College of Rheumatology Fibromyalgia Criteria
- NRS for average pain intensity over the past 24 hours
- Demographic characteristics (age, sex, race, and ethnicity)
- Medical history
- Prior (within last 30 days) and concomitant medications
- Height and body weight
- Sitting vital signs (blood pressure and pulse after 5 minutes)
- Complete physical examination, including comprehensive neurological examination
- Electrocardiogram after 5 minutes in supine position
- Urine pregnancy test for females of childbearing potential
- Urine drug test
- Breathalyzer test for alcohol
- Blood samples for fasting (8 hours) serum chemistry HIV, hepatitis B surface antigen, hepatitis C antibody, triglycerides, and hematology (including HbA1c)
- Urine sample for urinalysis
- HADS
- S-STS
- Adverse events

Eligible subjects who meet all inclusion and exclusion criteria will enter the 1- to 4-week Screening Period. The following procedures and assessments will be performed:

- Subjects who are taking more than 1 analgesic medication will discontinue all but 1 of the medications as allowed by the protocol before the start of daily pain and sleep evaluations. The duration of their Screening Period will depend on the time required to discontinue analgesic medications, but the total duration of the Screening Period cannot exceed 4 weeks. Subjects who are taking no more than 1 allowed analgesic medication will begin daily pain and sleep evaluations at bedtime immediately after Visit 1 (i.e., will begin Week -1).
- Subjects will be provided a handheld device, and as a method for ensuring consistency and reliability of pain scoring, instructed on how to record their pain on the device

 Subjects will also be educated on appropriate expectations around their participation in a clinical study

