7.3 Subject Inclusion and Exclusion Criteria

Inclusion and exclusion criteria will be provided in a subject listing where each subject number not meeting each criterion will be displayed.

MPB Biostats

In order for a subject to be randomized, the subject's mean NRS score assessing average pain intensity in the past 24 hours and diary compliance will be used to assess the following inclusion criteria for randomization:

Subject listings will include the treatment arm, protocol amendment version(s), was the subject rescreened (yes/no), and inclusion/exclusion criteria numbers not met. Subjects will be given "Screen Fail" as the treatment arm unless the subject was randomized to a study treatment. Any subjects that may have been randomized to a study treatment in error due to failure to pass the inclusion/exclusion criteria will be reported as protocol deviations. The numbers of the inclusion/exclusion criteria not met will list the protocol amendment version number and a brief description of the inclusion/exclusion criteria. Subject's meeting all inclusion/exclusion criteria, at screening but failing the inclusion criteria for randomization will not be given a number. Therefore, only "Randomization Ineligible" will be presented in the subject disposition tables and listings.

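### Protocol 10.2 lists the Visit 2 S-STS only for subjects already randomized, although exclusion 21 depends on that score, and Protocol 10.3.1 leaves out the Week 2 S-STS

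*Protocol*

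**What the plan says.** **Visit 2.** Exclusion 21 in Protocol 7.2 applies to subjects who meet the suicidality thresholds "based on the S-STS at Visit 1 or Visit 2". The synopsis has the same criterion and adds "Waivers to the exclusion criteria will NOT be allowed". For the Baseline Visit, Protocol 6.1 states that "study personnel will verify eligibility with the inclusion and exclusion criteria when the subjects are on site, and prior to randomization". Protocol 10.2 divides the visit into two lists. The list for everyone attending includes the urine drug test, the breathalyzer, sensory testing and the automated check of pain scores and diary compliance. The other list, which contains the S-STS, is introduced by "Subjects who continue to meet all entry criteria and are randomized by the interactive response technology system will undergo the following procedures and assessments".

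**Week 2.** The synopsis, Protocol 6.1, Table 3 and SAP Appendix I schedule the S-STS at Visit 3, and SAP 10.6.1 includes Week 2 among the visits to be summarized. The Visit 3 list in Protocol 10.3.1 has the PGI-C and the Insomnia Severity Index but no S-STS.

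**The concern.** The heading in Section 10.2 is circular. A result needed to confirm that a subject still meets the entry criteria is listed only for subjects who have been confirmed and randomized. A site following that list could randomize someone who then meets an exclusion that cannot be waived. SAP 7.3 deals with such cases after the fact: subjects "randomized to a study treatment in error due to failure to pass the inclusion/exclusion criteria will be reported as protocol deviations".

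At Week 2, a site working from Section 10.3.1 could skip a suicidality assessment that the rest of the plan expects, leaving a hole in the Week 2 summary. Section 10 is not merely background here, because Protocol 9.3.1 names either Table 3 or Section 10 as the source for safety time points.

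**Working it through.** This is mainly a comparison of text. The documents state no figure to reproduce.

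**Step 1. Which entry criteria need a Visit 2 result?** Of the 21 exclusion criteria in Protocol 7.2, two name Visit 2:

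| Criterion | Test | Place in Section 10.2 |
|---|---|---|
| 16: "Positive urine drug screen for marijuana, opioids, any benzodiazepines inconsistent with current prescriptions, or breathalyzer test for alcohol at Visit 2" | Urine drug test, breathalyzer | List for all subjects at Visit 2 |
| 21 | S-STS | Only the list for randomized subjects |

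So for 1 of these 2 criteria, the test is listed only after randomization.

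**Step 2. How is Visit 1 handled?** Protocol 10.1 lists the S-STS among the Visit 1 procedures and only afterwards says "Eligible subjects who meet all inclusion and exclusion criteria will enter the 1- to 4-week Screening Period". There the score comes before the eligibility decision, so the two visits are treated differently.

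**Step 3. Does another passage fix the order at Visit 2?**
- Protocol 6.1 says "The following scales will be completed at the Baseline Visit: BPI-DPN, the SF-MPQ-2, the QOL-DN, the HADS, the Insomnia Severity Index, and the S-STS". This names the visit but not the position relative to randomization, and the sentence follows the text on randomization and dispensing.
- The order of the Section 6.1 narrative cannot be relied on. It describes blood sampling before randomization and sensory testing after it, whereas Section 10.2 does the reverse.
- Table 3 and SAP Appendix I show only the visit.
- The interactive response technology check, as described in Protocol 6.1, 10.2 and 12.2, uses pain scores, their variability and diary compliance. No passage says that it receives the S-STS.

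No passage places the Visit 2 S-STS before randomization.

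**Step 4. Count the S-STS across Section 10.** Table 3 schedules it at Visits 1 to 4.

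| Visit | Section 10 |
|---|---|
| 1 | Listed before the eligibility decision (10.1) |
| 2 | Listed for randomized subjects only (10.2) |
| 3 | Absent (10.3.1) |
| 4 | Listed (10.3.2) |

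It is misplaced or missing at 2 of 4 visits. At Week 2, 1 of 3 scheduled scales is missing. Of the two scheduled post-baseline S-STS assessments (Weeks 2 and 4), 1 is missing.

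**Step 5. Intervals between scheduled S-STS assessments.** Table 3 sets Baseline at Day 1, Week 2 at Day 14 ± 2 (Days 12 to 16) and Week 4 at Day 28 ± 2 (Days 26 to 30).
- Day 1 to Week 2: 12 − 1 = 11 to 16 − 1 = 15 days
- Week 2 to Week 4: 26 − 16 = 10 to 30 − 12 = 18 days
- Day 1 to Week 4 with Week 2 missed: 26 − 1 = 25 to 30 − 1 = 29 days

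The longest scheduled gap from Day 1 onward is therefore 18 days with the Week 2 assessment and 25 to 29 days without it.

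**The case against.** The strongest reply is that the governing rule is already clear. Section 6.1 requires verification before randomization, exclusion 21 names Visit 2, and the Section 10.2 heading itself speaks of subjects who still meet the criteria. A site can satisfy all three only by completing the S-STS beforehand, so what is left is a misplaced bullet. Moreover, the S-STS is third in its list and dispensing of investigational product is eighth. If list order means anything, the score would be available before drug is handed over. A subject then withheld from treatment would fall in the SAP 7.1 category of randomized but not treated, and outside both the Safety and the Efficacy Populations. On Week 2, several other places schedule the assessment, and Section 10 itself opens by pointing to Table 3. The 10.3.1 list also shows copying wear elsewhere: it times the next telephone call from Week 0, where Section 6.1 times it from the Week 2 visit.

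Much of this stands. The Section 6.1 rule is clear, the Week 2 gap is a drafting omission, and the S-STS is listed ahead of dispensing. It does not remove the conflict. The bullets in 10.2 are not stated to be sequential, no instruction to withhold drug accompanies them, and randomizing a subject who meets an exclusion is a deviation whether or not drug is dispensed.

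**Conclusion.** The inconsistency is real in both places. Section 10.2, followed literally, allows randomization before the Visit 2 S-STS result exists, contrary to exclusion 21 and Section 6.1. Section 10.3.1 omits an assessment required elsewhere in both documents.

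The practical size is probably small. The documents give no rate of subjects who first meet exclusion 21 at Visit 2, but everyone reaching that visit has already passed the S-STS at Visit 1 and the psychiatric exclusions. If the Week 2 S-STS were missed, adverse events would still be assessed at Visit 3 and in the weekly telephone contacts. The 25 to 29 day gap assumes that a site works from Section 10.3.1 alone. There is no effect on type I error, power or the primary analysis. The point should still be corrected, because these are working procedure lists that give the wrong result if followed, on a suicidality criterion that allows no waiver.

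**What to change.** Reconcile the Section 10.2 lists with exclusion 21 (synopsis and Protocol 7.2) and with the verification rule in the synopsis and Section 6.1, so that the protocol gives one order for the Visit 2 S-STS and randomization. Reconcile the Section 10.3.1 list with the synopsis, Section 6.1, Table 3 and SAP Appendix I on the Week 2 S-STS.

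The cost is two list edits in a written amendment submitted for IRB review under Protocol 13.4. The S-STS is already scheduled at both visits, so no procedure is added, and the SAP needs no change.

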10.3 Treatment Period (Week 2 and Week 4)

10.3.1 Week 2 (Visit 3)

At Visit 3, the following procedures and assessments will be performed:

- Concomitant medication use assessed
- Adverse events assessed
- Sitting vital signs (blood pressure and pulse after 5 minutes)
- Serum chemistry for liver function testing (only)
- PGI-C
- Insomnia Severity Index
- Rescue medication supplies returned, appropriate use assessed, and compliance/accountability performed
- Investigational product and supplies returned and compliance/accountability performed
- Compliance with entry of pain intensity and rescue medication into daily diary
- Investigational product dispensed
- Rescue medication dispensed

Subjects will be reminded on how to record their pain on the device

Subjects will also be reminded about appropriate expectations around their participation in a clinical study

Review of these educational materials may be repeated for some or all subjects depending on findings of an ongoing blinded data review (e.g., if pain score variability is increased on a subject or site level. On each of day until returning to the study site at Week 4, subjects will record the following on the handheld device:

- At bedtime: average pain intensity, worst pain intensity, pain on walking, and use of rescue medication during the past 24 hours.
- Upon waking: DSIS

The investigative site staff will contact study subjects by telephone one week following Week 0 to reinforce the diary completion and assess adverse events.

Subjects will be instructed to return to the study site at Week 4.

